5 APPENDIX

Sample size details

The % in each study group was based on estimates from the steering committee. It was assumed 1/3 would be enrolled in India, 1/3 in China, and 1/3 in the rest of the world. The table below shows the estimates from steering committee members, and the overall estimate, which was derived in a non-formalistic way from the physicians' estimates.

Physician	%Secondary		% Implanted					
			Secondary		1.5		1.0	
	My center	Others in my country	My center	Other centers in my country	My center	Other centers in my country	My center	Other centers in my country
[name] (Belarus)	75	No ans.	98	90	65	65	40	40
[name] (India)	70	80	80	10-80	No answer		15	15
[name] (China)	50	50	50	15	60	25	40	10
[name] (China)	30	55	50	30	40	30	30	30
Overall estimate	60*		57		45		22	

* Takes into account efforts to promote enrolling primary prevention subjects.

[figure not shown]
The program sim.sas produced power calculations based on the sample size assumptions. The program was run feeding in sample sizes from 4000-5000. Each study sample size was simulated 10,000 times, and the resulting power (% of time the lower one-sided 95% confidence limit of the hazard ratio (HR) was above 0.70) and the average hazard ratio for the 10,000 simulations are shown.

Sample size	Power	HR
4000	73.6	0.904
4050	74.9	0.904
4100	75.2	0.904
4150	74.6	0.903
4200	76.0	0.905
4250	75.6	0.904
4300	77.6	0.905
4350	76.7	0.903
4400	77.7	0.904
4450	78.1	0.903
4500	78.2	0.903
4550	79.2	0.904
4600	79.0	0.904
4650	79.5	0.905
4700	79.9	0.903
4750	80.5	0.903
4800	80.4	0.903
4850	80.6	0.902
4900	81.6	0.904
4950	81.8	0.904
5000	82.3	0.903

HR is included because those further away from 0.91 are under-estimating power.

4800 was chosen because the 4750 estimate of 80.5 may be too high (compared to 4700 and 4800).

Here is a screen shot of PASS mortality calculations

PROGRAM SIM.SAS

```
*****  
*****  
Program Name: SIM.SAS  
  
Study: IMPROVE SCA  
  
Purpose: Determining study sample size  
  
Inputs: None  
  
Outputs: None  
  
Cautions: None  
  
Revision  
History: Version Date Author Description  
----- ----- ----- -----  
-----  
1 09DEC13 [name] Initial  
Version  
*****  
*****/
```

```
OPTIONS PS=56;
```

```
/*  
SS: TOTAL SAMPLE SIZE OF STUDY  
PROBSEC: PROBABILITY OF SECONDARY (AS OPPOSED TO PRIMARY) PREVENTION  
PROB15: PROBABILITY OF BEING 1.5 GIVEN THEY ARE PRIMARY  
IMPSEC: PROBABILITY THAT A SECONDARY PREVENTION PATIENT GETS AN IMPLANT  
IMP15: PROBABILITY THAT A 1.5 PATIENT GETS AN IMPLANT  
IMPPRIM: PROBABILITY THAT A PRIMARY (NON-1.5) PATIENT GETS AN IMPLANT  
FAILA12: PROBABILITY THAT A GROUP A PATIENT WILL HAVE AN APPROPRIATE VT/VF IN  
THE FIRST 12 MONTHS  
FAILALONG: PROBABILITY THAT A GROUP A PATIENT WILL HAVE AN APPROPRIATE VT/VF  
IN A GIVEN YEAR IN ANY YEAR AFTER THE FIRST 12 YEAR  
HRAC: ASSUMED HAZARD RATIO OF GROUP A TO GROUP C  
HRCE: ASSUMED HAZARD RATIO OF GROUP C TO GROUP E  
YEARSENROLL: YEARS TO GET FULL ENROLLMENT  
YEARLYATTRITION: ANNUAL ATTRITION DUE TO DEATH OR EXIT (IMPLANTED GROUPS A,  
C, AND E ONLY)  
YEARSFOLLOW: YEARS OF FOLLOW-UP FOLLOWING THE LAST ENROLLMENT  
*/
```

```
%MACRO STUDY (  
SS,  
PROBSEC,  
PROB15,  
IMPSEC,  
IMP15,  
IMPPRIM,  
FAILA12,  
FAILALONG,  
HRAC,  
HRCE,  
YEARSENROLL,
```

```

YEARLYATTRITION,
YEARSFOLLOW);

DATA STUDY;
DO PT=1 TO &SS;
  IMPDT=.; ENDDT=.; ATRTIME=.; FAILTIME=.; FAIL=.; SURVTIME=.;
  *ICD INDICATION;
  A=RAND('UNIFORM');
  IF A<&PROBSEC THEN IND='SECONDARY'; ELSE IND='PRIMARY';

  *1.0 OR 1.5?;
  B=RAND('UNIFORM');
  IF B<&PROB15 THEN LEVEL='1.5'; ELSE LEVEL='1.0';

  *ACCEPT IMPLANT?;
  C=RAND('UNIFORM');
  IF IND='SECONDARY' THEN DO;
    IF C<&IMPSEC THEN IMP=1; ELSE IMP=0;
  END;
  IF IND='PRIMARY' THEN DO;
    IF LEVEL='1.5' THEN DO;
      IF C<&IMP15 THEN IMP=1; ELSE IMP=0;
    END;
    IF LEVEL='1.0' THEN DO;
      IF C<&IMPPRIM THEN IMP=1; ELSE IMP=0;
    END;
  END;
  IF IND='SECONDARY' AND IMP=1 THEN GROUP='A';
  IF IND='SECONDARY' AND IMP=0 THEN GROUP='B';
  IF IND='PRIMARY' AND LEVEL='1.5' AND IMP=1 THEN GROUP='C';
  IF IND='PRIMARY' AND LEVEL='1.5' AND IMP=0 THEN GROUP='D';
  IF IND='PRIMARY' AND LEVEL='1.0' AND IMP=1 THEN GROUP='E';
  IF IND='PRIMARY' AND LEVEL='1.0' AND IMP=0 THEN GROUP='F';

  *GET 10-YEAR PROBABILITY OF APPROPRIATE THERAPY (ASSUMING NO DEATH, EXIT,
OR END OF STUDY);
  FAILMONTH=.;
  DO MONTH=1 TO 120; *MONTHS;
    *MORE FAILURES IN FIRST YEAR;
    D=RAND('UNIFORM');
    IF GROUP='A' AND FAILMONTH=. THEN DO;
      IF MONTH LE 12 THEN DO;
        IF D<1-(1-&FAILA12)**(1/12) THEN FAILMONTH=MONTH;
      END;
      IF MONTH>12 THEN DO;
        IF D<1-(1-&FAILALONG)**(1/12) THEN FAILMONTH=MONTH;
      END;
    END;
    IF GROUP='C' AND FAILMONTH=. THEN DO;
      IF MONTH LE 12 THEN DO;
        IF D<1-(1-&FAILA12*&HRAC)**(1/12) THEN FAILMONTH=MONTH;
      END;
      IF MONTH>12 THEN DO;
        IF D<1-(1-&FAILALONG*&HRAC)**(1/12) THEN FAILMONTH=MONTH;
      END;
    END;
  END;

```

```

        IF GROUP='E' AND FAILMONTH=. THEN DO;
          IF MONTH LE 12 THEN DO;
            IF D<1-(1-&FAILA12*&HRAC*&HRCE) ** (1/12) THEN FAILMONTH=MONTH;
          END;
          IF MONTH>12 THEN DO;
            IF D<1-(1-&FAILALONG*&HRAC*&HRCE) ** (1/12) THEN
              FAILMONTH=MONTH;
          END;
        END;
      END;

      E=RAND('UNIFORM');
      FAILTIME=ROUND((FAILMONTH-1)*365.25/12+E*30);

*CENSOR PATIENTS ALONG THE WAY;
*JAN 1, 2014 IS FIRST POSSIBLE DATE OF IMPLANT;
FORMAT IMPDT ENDDT LASTSTUDYDT DATE7.;
IF GROUP IN ('A','C','E') THEN DO;
  *ASSUME SLOW ENROLLMENT TO BEGIN, WITH INCREASING ENROLLMENT OVER
  REST OF TIME PERIOD;
  F=RAND('CHISQ',2);
  IF F>4 OR F<0.1 THEN F=RAND('CHISQ',2);
  IF F>4 OR F<0.1 THEN F=RAND('CHISQ',2);
  IF F>4 OR F<0.1 THEN F=RAND('CHISQ',2);
  *ABOVE WILL CAPTURE>99%. FOR A FEW, JUST GIVE A MIDDLE VALUE;
  IF F>4 OR F<0.1 THEN F=1+E;
  XX=(F*(-1/3.9)+4/3.9);
  IMPDT='01JAN14'D+ROUND((F*(-1/3.9)+4/3.9)*(&YEARSENROLL*365.25));
END;

*ATTRITION DUE TO DEATH/EXIT;
ATRMONTH=.;
DO MONTH=1 TO 120;
  G=RAND('UNIFORM');
  IF ATRMONTH=. AND G<1-(1-&YEARLYATTRITION) ** (1/12) THEN
    ATRMONTH=MONTH;
  END;
  H=RAND('UNIFORM');
  ATRTIME=ROUND((ATRMONTH-1)*365.25/12+H*30);

*FIND OUT ATTRITION DATE AND EVENT DATE, THEN USE THE EARLIER OF THE
TWO;
  IF FAILTIME NE . AND ATRTIME NE . THEN
    ENDDT=IMPDT+MIN(FAILTIME,ATRTIME);
  IF FAILTIME = . AND ATRTIME NE . THEN ENDDT=IMPDT+ATRTIME;
  IF FAILTIME NE . AND ATRTIME = . THEN ENDDT=IMPDT+FAILTIME;
  IF FAILTIME = . AND ATRTIME = . THEN ENDDT=IMPDT+3653;
  IF ENDDT=IMPDT+FAILTIME AND FAILTIME NE . THEN FAIL=1; ELSE
    FAIL=0;

*GET END OF STUDY;
ENDSTUDYDT='01JAN14'D+INT((&YEARSENROLL+&YEARSFOLLOW)*365.25);
*ASSUME LAST FOLLOW-UP WILL BE WITHIN 3 MONTHS OF END STUDY;
I=RAND('UNIFORM');

```

```

LASTSTUDYDT=ENDSTUDYDT-INT(I*91);

IF ENDDT>LASTSTUDYDT THEN DO;
  ENDDT=LASTSTUDYDT;
  FAIL=0;
  END;

  SURVTIME=(ENDDT-IMPDT)/365.25*12;
END;

*FOR PHREG SO THE HR IS C/A;
GROUP2=' ';
IF GROUP='C' THEN GROUP2=' C';
IF GROUP='A' THEN GROUP2='A';
IF GROUP='E' THEN GROUP2=' E';

OUTPUT;
END;
RUN;

ODS LISTING CLOSE;
PROC LIFETEST timelist=(12,24,36) DATA=STUDY;
STRATA GROUP;
TIME SURVTIME*FAIL(0);
SURVIVAL out=CI conftype=loglog stderr;
RUN;

DATA CI;
SET CI;
FAILURE=1-SURVIVAL;
FUCL=1-SDF_LCL;
FLCL=1-SDF_UCL;
RUN;

DATA CI12;
SET CI;
WHERE SDF_LCL NE . AND SURVTIME<12;
RUN;

PROC SORT;
BY GROUP SURVTIME;
RUN;

DATA CI12;
SET CI12;
BY GROUP SURVTIME;
IF NOT LAST.GROUP THEN DELETE;
RUN;

DATA CI24;
SET CI;
WHERE SDF_LCL NE . AND SURVTIME<24;
RUN;

PROC SORT;
BY GROUP SURVTIME;
RUN;

```

```

DATA CI24;
SET CI24;
BY GROUP SURVTIME;
IF NOT LAST.GROUP THEN DELETE;
RUN;

DATA CI36;
SET CI;
WHERE SDF_LCL NE . AND SURVTIME<36;
RUN;

PROC SORT;
BY GROUP SURVTIME;
RUN;

DATA CI36;
SET CI36;
BY GROUP SURVTIME;
IF NOT LAST.GROUP THEN DELETE;
RUN;

PROC PHREG DATA=STUDY;
WHERE GROUP IN ('A', 'C');
CLASS GROUP2;
*ALPHA=0.1 GIVES ONE-SIDED 95% CONFIDENCE INTERVAL;
MODEL SURVTIME*FAIL(0)=GROUP2 / RL ALPHA=0.1;
ODS OUTPUT ParameterEstimates=HRAC;
RUN;

PROC PHREG DATA=STUDY;
WHERE GROUP IN ('E', 'C');
CLASS GROUP2;
MODEL SURVTIME*FAIL(0)=GROUP2 / RL;
ODS OUTPUT ParameterEstimates=HRCE;
RUN;

PROC PHREG DATA=STUDY;
WHERE GROUP IN ('A', 'E');
CLASS GROUP2;
MODEL SURVTIME*FAIL(0)=GROUP2 / RL;
ODS OUTPUT ParameterEstimates=HRAE;
RUN;

PROC LIFETEST DATA=STUDY;
WHERE GROUP IN ('A', 'E');
STRATA GROUP;
TIME SURVTIME*FAIL(0);
ODS OUTPUT HomTests=LOGRANKAE;
RUN;

PROC LIFETEST DATA=STUDY;
WHERE GROUP IN ('C', 'E');
STRATA GROUP;
TIME SURVTIME*FAIL(0);
ODS OUTPUT HomTests=LOGRANKCE;
RUN;

```

```

PROC FREQ DATA=STUDY NOPRINT;
TABLES GROUP / OUT=GROUPN;
RUN;
ODS LISTING;

DATA STUDYRES;
MERGE
CI12 (WHERE=(GROUP='A') RENAME=(FAILURE=FAIL_A12 FLCL=FLCL_A12 FUCL=FUCL_A12)
KEEP=GROUP FAILURE FLCL FUCL)
CI12 (WHERE=(GROUP='C') RENAME=(FAILURE=FAIL_C12 FLCL=FLCL_C12 FUCL=FUCL_C12)
KEEP=GROUP FAILURE FLCL FUCL)
CI12 (WHERE=(GROUP='E') RENAME=(FAILURE=FAIL_E12 FLCL=FLCL_E12 FUCL=FUCL_E12)
KEEP=GROUP FAILURE FLCL FUCL)
CI24 (WHERE=(GROUP='A') RENAME=(FAILURE=FAIL_A24 FLCL=FLCL_A24 FUCL=FUCL_A24)
KEEP=GROUP FAILURE FLCL FUCL)
CI24 (WHERE=(GROUP='C') RENAME=(FAILURE=FAIL_C24 FLCL=FLCL_C24 FUCL=FUCL_C24)
KEEP=GROUP FAILURE FLCL FUCL)
CI24 (WHERE=(GROUP='E') RENAME=(FAILURE=FAIL_E24 FLCL=FLCL_E24 FUCL=FUCL_E24)
KEEP=GROUP FAILURE FLCL FUCL)
CI36 (WHERE=(GROUP='A') RENAME=(FAILURE=FAIL_A36 FLCL=FLCL_A36 FUCL=FUCL_A36)
KEEP=GROUP FAILURE FLCL FUCL)
CI36 (WHERE=(GROUP='C') RENAME=(FAILURE=FAIL_C36 FLCL=FLCL_C36 FUCL=FUCL_C36)
KEEP=GROUP FAILURE FLCL FUCL)
CI36 (WHERE=(GROUP='E') RENAME=(FAILURE=FAIL_E36 FLCL=FLCL_E36 FUCL=FUCL_E36)
KEEP=GROUP FAILURE FLCL FUCL)
HRAC (RENAME=(HAZARDRATIO=HR_AC HRLOWERCL=HRL_AC HRUPPERCL=HRU_AC)
KEEP=HAZARDRATIO HRLOWERCL HRUPPERCL)
HRCE (RENAME=(HAZARDRATIO=HR_CE HRLOWERCL=HRL_CE HRUPPERCL=HRU_CE)
KEEP=HAZARDRATIO HRLOWERCL HRUPPERCL)
HRAE (RENAME=(HAZARDRATIO=HR_AE HRLOWERCL=HRL_AE HRUPPERCL=HRU_AE)
KEEP=HAZARDRATIO HRLOWERCL HRUPPERCL)
LOGRANKAE (WHERE=(TEST='Log-Rank') RENAME=(ProbChiSq=LOGRANKAE) KEEP=TEST
ProbChiSq)
LOGRANKCE (WHERE=(TEST='Log-Rank') RENAME=(ProbChiSq=LOGRANKCE) KEEP=TEST
ProbChiSq)
GROUPN (WHERE=(GROUP='A') RENAME=(COUNT=GROUPA_SS) KEEP=GROUP COUNT)
GROUPN (WHERE=(GROUP='B') RENAME=(COUNT=GROUPB_SS) KEEP=GROUP COUNT)
GROUPN (WHERE=(GROUP='C') RENAME=(COUNT=GROUPC_SS) KEEP=GROUP COUNT)
GROUPN (WHERE=(GROUP='D') RENAME=(COUNT=GROUPD_SS) KEEP=GROUP COUNT)
GROUPN (WHERE=(GROUP='E') RENAME=(COUNT=GROUPE_SS) KEEP=GROUP COUNT)
GROUPN (WHERE=(GROUP='F') RENAME=(COUNT=GROUPF_SS) KEEP=GROUP COUNT)
;

DROP GROUP TEST;
RUN;

%MEND;

```

%% ASSUMPTIONS CAME FROM QUESTIONS ASKED OF 2 CHINESE, 1 INDIAN, AND 1 BELARUSSION PHYSICIANS. THEY WERE ASKED TO ESTIMATE %
 AT THEIR CENTER, THEN IN THE REST OF THEIR COUNTRY. IT IS ASSUMED THAT 1/3 OF THE PTS WILL BE CHINA, 1/3 INDIA, AND 1/3 THE REST.

% OF SECONDARY:
 [name]: 75% HIS CENTER / 75% OTHERS

```

[name]: 70/80
[name]: 50/50
[name]: 30/55
52% CHINA, 78% INDIA, AND 75% ROW = 68%

% OF SECONDARY THAT GET IMPLANTED:
[name]: 98/90
[name]: 80/45
[name]: 50/15
[name]: 50/30
30% CHINA, 50% INDIA, 91% ROW = 57%

% OF 1.5 THAT GET IMPLANTED:
[name]: 65/65
[name]: NO GUESS
[name]: 60/25
[name]: 40/30
30% CHINA, 40% INDIA, 65% ROW = 45%

% OF 1.0 THAT GET IMPLANTED:
[name]: 40/40
[name]: 15/5
[name]: 40/10
[name]: 30/30
20% CHINA, 6% INDIA, 40% ROW = 22%
;

%MACRO LOOP(NUM,SS,PROBSEC,YEARSENROLL,YEARSFOLLOW);
DATA ALLSTUDIES;
RUN;

%DO X = 1 %TO &NUM;
%STUDY(
SS=&SS,
PROBSEC=&PROBSEC,
PROB15=0.5,
IMPSEC=0.57,
IMP15=0.45,
IMPPRIM=0.22,
/*FAIL VARIABLES BELOW WERE CHOSEN TO BEST MATCH THE 12-MONTH FAILURE RATES
AND THE HAZARD RATIOS IN OMNI.  HR OF C TO A WAS 0.909.  HR OF E TO C WAS
0.678*/
FAILA12=0.225,
FAILALONG=0.1110,
HRAC=0.91,
HRCE=0.68,
YEARSENROLL=&YEARSENROLL,
YEARLYATTRITION=0.1,
YEARSFOLLOW=&YEARSFOLLOW);

DATA ALLSTUDIES;
SET ALLSTUDIES STUDYRES;
RUN;
%END;

DATA RESULTS;
SET ALLSTUDIES;

```

```

WHERE FAIL_A12 NE .;

*IF WE WANT STUDY RESULT TO BE THAT C IS CLOSER TO A THAN IT IS TO E;
  *BASED ON DIFFERENCES AT 36 MONTHS.  TOO UNSTABLE TO USE: SOMETIMES
FAIL_E > FAIL_C, YET HR_CE IS STILL <1;
/*      DIFFAC=FAIL_A-FAIL_C; */
/*      DIFFCE=FAIL_C-FAIL_E; */
/*      IF FAIL_E>0 THEN DO; */
/*          IF DIFFCE>DIFFAC THEN OBS_SUCCESS=1; ELSE OBS_SUCCESS=0; */
/*      END; */
/*      ELSE DO; */
/*          IF DIFFAC<0.04 THEN OBS_SUCCESS=1; ELSE OBS_SUCCESS=0;      */
/*      END; */

IF HR_AC>1 THEN OBS_SUCCESS2=1;
ELSE IF FAIL_E12>0 THEN DO;
  IF HR_AC > HR_CE THEN OBS_SUCCESS2=1; ELSE OBS_SUCCESS2=0;
END;
ELSE DO;
  IF HR_AC> 0.9 THEN OBS_SUCCESS2=1; ELSE OBS_SUCCESS2=0;
END;
LABEL OBS_SUCCESS2='SUCESSFUL TRIAL?  SUCCESS BASICALLY DEFINED AS HR OF
C TO A HIGHER THAN E TO C';

*NON-INFERIORITY TEST - MARGINS OF 20, 25, AND 30%;
  IF HRL_AC>0.7 THEN NONINF70=1; ELSE NONINF70=0;
  IF HRL_AC>0.75 THEN NONINF75=1; ELSE NONINF75=0;
  IF HRL_AC>0.8 THEN NONINF80=1; ELSE NONINF80=0;
  IF HRL_AC>0.85 THEN NONINF85=1; ELSE NONINF85=0;
  IF HRL_AC>0.9 THEN NONINF90=1; ELSE NONINF90=0;

*SUPCESS IF 2.0 IS HIGHER THAN 1.0 AND 1.5 IS HIGHER THAN 1.0;
  IF LOGRANKAE<0.05 AND LOGRANKCE<0.05 AND HR_CE<1 THEN SUPSUCCESS=1;
  ELSE IF LOGRANKAE<0.05 AND HR_AE<1 THEN SUPSUCCESS=0.2;
  ELSE IF LOGRANKCE<0.05 AND HR_CE<1 THEN SUPSUCCESS=0.1;
  ELSE SUPSUCCESS=0;

*OPC SUCCESS;
IF FLCL_C12>0.15 THEN OPC15SUCCESS12=1; ELSE OPC15SUCCESS12=0;
IF FLCL_C24>0.15 THEN OPC15SUCCESS24=1; ELSE OPC15SUCCESS24=0;
IF FLCL_C36>0.15 THEN OPC15SUCCESS36=1; ELSE OPC15SUCCESS36=0;
IF FLCL_C12>0.20 THEN OPC20SUCCESS12=1; ELSE OPC20SUCCESS12=0;
IF FLCL_C24>0.20 THEN OPC20SUCCESS24=1; ELSE OPC20SUCCESS24=0;
IF FLCL_C36>0.20 THEN OPC20SUCCESS36=1; ELSE OPC20SUCCESS36=0;
IF FLCL_C12>0.25 THEN OPC25SUCCESS12=1; ELSE OPC25SUCCESS12=0;
IF FLCL_C24>0.25 THEN OPC25SUCCESS24=1; ELSE OPC25SUCCESS24=0;
IF FLCL_C36>0.25 THEN OPC25SUCCESS36=1; ELSE OPC25SUCCESS36=0;

*NARROW CONFIDENCE INTERVAL SUCCESS;
CIWIDTH12=FUCL_C12-FLCL_C12;
CIWIDTH24=FUCL_C24-FLCL_C24;
CIWIDTH36=FUCL_C36-FLCL_C36;
IF CIWIDTH12<0.05 THEN CI05SUCCESS12=1; ELSE CI05SUCCESS12=0;
IF CIWIDTH24<0.05 THEN CI05SUCCESS24=1; ELSE CI05SUCCESS24=0;
IF CIWIDTH36<0.05 THEN CI05SUCCESS36=1; ELSE CI05SUCCESS36=0;
IF CIWIDTH12<0.08 THEN CI08SUCCESS12=1; ELSE CI08SUCCESS12=0;
IF CIWIDTH24<0.08 THEN CI08SUCCESS24=1; ELSE CI08SUCCESS24=0;

```

```

IF CIWIDTH36<0.08 THEN CI08SUCCESS36=1; ELSE CI08SUCCESS36=0;
IF CIWIDTH12<0.10 THEN CI10SUCCESS12=1; ELSE CI10SUCCESS12=0;
IF CIWIDTH24<0.10 THEN CI10SUCCESS24=1; ELSE CI10SUCCESS24=0;
IF CIWIDTH36<0.10 THEN CI10SUCCESS36=1; ELSE CI10SUCCESS36=0;
IF CIWIDTH12<0.12 THEN CI12SUCCESS12=1; ELSE CI12SUCCESS12=0;
IF CIWIDTH24<0.12 THEN CI12SUCCESS24=1; ELSE CI12SUCCESS24=0;
IF CIWIDTH36<0.12 THEN CI12SUCCESS36=1; ELSE CI12SUCCESS36=0;
IF CIWIDTH12<0.15 THEN CI15SUCCESS12=1; ELSE CI15SUCCESS12=0;
IF CIWIDTH24<0.15 THEN CI15SUCCESS24=1; ELSE CI15SUCCESS24=0;
IF CIWIDTH36<0.15 THEN CI15SUCCESS36=1; ELSE CI15SUCCESS36=0;
RUN;

TITLE "SAMPLE SIZE IS &SS, PROBSEC=&PROBSEC, YEARS OF ENROLLMENT:
&YEARENROLL, YEARS OF FOLLOW-UP: &YEARSFOLLOW";

PROC FREQ;
TABLES OBS_SUCCESS2 NONINF70 NONINF75
OPC15SUCCESS12 OPC15SUCCESS24 OPC15SUCCESS36
OPC20SUCCESS12 OPC20SUCCESS24 OPC20SUCCESS36
OPC25SUCCESS12 OPC25SUCCESS24 OPC25SUCCESS36
CI05SUCCESS12 CI05SUCCESS24 CI05SUCCESS36
CI08SUCCESS12 CI08SUCCESS24 CI08SUCCESS36
CI10SUCCESS12 CI10SUCCESS24 CI10SUCCESS36
CI12SUCCESS12 CI12SUCCESS24 CI12SUCCESS36
CI15SUCCESS12 CI15SUCCESS24 CI15SUCCESS36;
RUN;

PROC MEANS N MEAN MEDIAN MAXDEC=3 DATA=ALLSTUDIES;
VAR FAIL_A12 FAIL_C12 FAIL_E12 FAIL_A24 FAIL_C24 FAIL_E24 HR_AC HR_CE
GROUPA_SS GROUPB_SS GROUPC_SS GROUPD_SS GROUPE_SS GROUPF_SS;
RUN;
%MEND;

```

```

%LOOP(10000, SS=4000, PROBSEC=0.6, YEARENROLL=1.97, YEARSFOLLOW=2);
%LOOP(10000, SS=4050, PROBSEC=0.6, YEARENROLL=1.99, YEARSFOLLOW=2);
%LOOP(10000, SS=4100, PROBSEC=0.6, YEARENROLL=2.01, YEARSFOLLOW=2);
%LOOP(10000, SS=4150, PROBSEC=0.6, YEARENROLL=2.02, YEARSFOLLOW=2);
%LOOP(10000, SS=4200, PROBSEC=0.6, YEARENROLL=2.04, YEARSFOLLOW=2);
%LOOP(10000, SS=4250, PROBSEC=0.6, YEARENROLL=2.06, YEARSFOLLOW=2);
%LOOP(10000, SS=4300, PROBSEC=0.6, YEARENROLL=2.07, YEARSFOLLOW=2);
%LOOP(10000, SS=4350, PROBSEC=0.6, YEARENROLL=2.09, YEARSFOLLOW=2);
%LOOP(10000, SS=4400, PROBSEC=0.6, YEARENROLL=2.11, YEARSFOLLOW=2);
%LOOP(10000, SS=4450, PROBSEC=0.6, YEARENROLL=2.12, YEARSFOLLOW=2);
%LOOP(10000, SS=4500, PROBSEC=0.6, YEARENROLL=2.14, YEARSFOLLOW=2);
%LOOP(10000, SS=4550, PROBSEC=0.6, YEARENROLL=2.16, YEARSFOLLOW=2);
%LOOP(10000, SS=4600, PROBSEC=0.6, YEARENROLL=2.18, YEARSFOLLOW=2);
%LOOP(10000, SS=4650, PROBSEC=0.6, YEARENROLL=2.19, YEARSFOLLOW=2);
%LOOP(10000, SS=4700, PROBSEC=0.6, YEARENROLL=2.21, YEARSFOLLOW=2);
%LOOP(10000, SS=4750, PROBSEC=0.6, YEARENROLL=2.23, YEARSFOLLOW=2);
%LOOP(10000, SS=4800, PROBSEC=0.6, YEARENROLL=2.24, YEARSFOLLOW=2);
%LOOP(10000, SS=4850, PROBSEC=0.6, YEARENROLL=2.26, YEARSFOLLOW=2);
%LOOP(10000, SS=4900, PROBSEC=0.6, YEARENROLL=2.28, YEARSFOLLOW=2);
%LOOP(10000, SS=4950, PROBSEC=0.6, YEARENROLL=2.29, YEARSFOLLOW=2);
%LOOP(10000, SS=5000, PROBSEC=0.6, YEARENROLL=2.31, YEARSFOLLOW=2);

```

```

/*
%macro plot(name);
%LOOP(1,SS=3000,YEARENROLL=1.6,YEARSFOLLOW=1);
DATA JJJ;
SET STUDY;
IF SURVTIME=. THEN DELETE;
IF GROUP='A' THEN G=1;
IF GROUP='C' THEN G=2;
IF GROUP='E' THEN G=3;
RUN;

PROC FORMAT;
VALUE type 1='A' 2='C' 3='E';
RUN;

PROC PRINT DATA=RESULTS;
VAR HR_AC     HR_CE;
RUN;

%MKMPlot(indata=JJJ,
          TRT=G,
          TRTfmt= TYPE.,
          PlotType=failure,
          SubjectID=PT,
          TimeToEvent=SURVTIME,
          EventIND=FAIL,
          Censored=0,
          ShowHazardRatio=Y,
          ShowLogRankPvalue=n,
          ShowCI=Y,
          SurvivalRateDataPointsSwap=y,
          xaxismax=36,xaxisby=6,
          Yaxismax=0.50,Yaxisby=.10,
          yaxislabel=%nrbquote(% with Appropriately Treated VT/VF),
          xaxislabel=%nrbquote(Months Since Implant),
          SubjectsatRiskBy=6,
          GraphfilePath=V:\Improve SCA\Sample Size,
          GraphFilename=&name,
          SurvivalRateDataPoints=12$24$36$48$60$72,
          StopPlotCount=20,
          AtRiskText=%str(Number Reamining)
          );
%mend;

%PLOT(SIM1);
%PLOT(SIM2);
%PLOT(SIM3);
%PLOT(SIM4);

```

```
%PLOT(SIM5);
%PLOT(SIM6);
%PLOT(SIM7);
%PLOT(SIM8);
%PLOT(SIM9);
%PLOT(SIM10);
%PLOT(SIM11);
%PLOT(SIM12);
%PLOT(SIM13);
%PLOT(SIM14);
%PLOT(SIM15);
%PLOT(SIM16);
%PLOT(SIM17);
%PLOT(SIM18);
%PLOT(SIM19);
%PLOT(SIM20);
```

```
/*
```

```
PROC LIFETEST DATA=STUDY;
STRATA GROUP;
TIME SURVTIME*FAIL(0);
RUN;

PROC FREQ DATA=STUDY;
TABLES IMPDT;
RUN;

PROC PRINT DATA=STUDY;
WHERE GROUP IN ('A','C','E') AND SURVTIME=.;
RUN;

PROC SORT DATA=STUDY;
BY IMPDT;
RUN;
```

```
PROC PRINT DATA=STUDY;
VAR PT IMPDT ENDDT FAILMONTH ATRMONTH SURVTIME FAIL;
RUN;
```

```
*GET A VS. C ONLY;
DATA JJJ;
SET STUDY;
IF SURVTIME=. THEN DELETE;
IF GROUP='E' THEN DELETE;
IF GROUP='A' THEN G=1;
```

```

IF GROUP='C' THEN G=2;
IF GROUP='E' THEN G=3;
RUN;

PROC FORMAT;
VALUE type 1='A' 2='C' 3='E';
RUN;

%MKMPlot(indata=JJJ,
      TRT=G,
      TRTfmt= TYPE.,
      PlotType=failure,
      SubjectID=PT,
      TimeToEvent=SURVTIME,
      EventIND=FAIL,
      Censored=0,
      ShowHazardRatio=Y,
      ShowLogRankPvalue=y,
      ShowCI=Y,
      SurvivalRateDataPointsSwap=y,
      xaxismax=36,xaxisby=6,
      Yaxismax=0.50,Yaxisby=.10,
      yaxislabel=%nrbquote(% with Appropriately Treated VT/VF),
      xaxislabel=%nrbquote(Months Since Implant),
      SubjectsatRiskBy=6,
      GraphfilePath=V:\Improve SCA\Sample Size,
      GraphFilename=SIMULATIONAC,
      SurvivalRateDataPoints=12$24$36$48$60$72,
      StopPlotCount=20,
      AtRiskText=%str(Number Reamining)
      );

```

```

*GET C VS. E ONLY;
DATA JJJ;
SET STUDY;
IF SURVTIME=. THEN DELETE;
IF GROUP='A' THEN DELETE;
IF GROUP='A' THEN G=1;
IF GROUP='C' THEN G=2;
IF GROUP='E' THEN G=3;
RUN;

```

```

PROC FORMAT;
VALUE type 1='A' 2='C' 3='E';
RUN;

%MKMPlot(indata=JJJ,
      TRT=G,
      TRTfmt= TYPE.,
      PlotType=failure,
      SubjectID=PT,
      TimeToEvent=SURVTIME,
      EventIND=FAIL,
      Censored=0,

```

```
ShowHazardRatio=Y,  
ShowLogRankPvalue=y,  
ShowCI=Y,  
SurvivalRateDataPointsSwap=y,  
    xaxismax=36,xaxisby=6,  
    Yaxismax=0.50,Yaxisby=.10,  
yaxislabel=%nrbquote(% with Appropriately Treated VT/VF),  
xaxislabel=%nrbquote(Months Since Implant),  
    SubjectsatRiskBy=6,  
    GraphfilePath=V:\Improve SCA\Sample Size,  
GraphFilename=SIMULATIONCE,  
SurvivalRateDataPoints=12$24$36$48$60$72,  
StopPlotCount=20,  
AtRiskText=%str(Number Reamining)  
);
```

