3.2 Primary Objective: Appropriate Therapy

The primary objective is to demonstrate that appropriate VT/VF therapy rates (shock and ATP) for subjects meeting 1.5 prevention criteria implanted with a Medtronic device (ICD/CRT-D) are equivalent (within 30%) to rates in subjects meeting secondary prevention criteria.

The primary objective will be evaluated by using post-implant time to first appropriate VT/VF therapy (shock and ATP). More specifically, the following hypothesis will be tested:

Hypothesis

H_0 : Hazard ratio of Implanted 1.5 patients to implanted secondary patients ≤ 0.70
 H_a : Hazard ratio of Implanted 1.5 patients to implanted secondary patients > 0.70

Endpoint Definition

The event of interest for this objective is appropriate VT/VF therapy. To qualify as an event, a VT/VF event observed by the ICD/CRT must be adjudicated to be one of the following by the Episode Review Committee:

- Polymorphic VT/VF
- Monomorphic VT
- Non-sustained VT/VF
- Other VT/VF, specify:

Additionally, the episode must have been treated either by ATP, shock, or both by the device.

Performance Requirement

The null hypothesis will be rejected if the one-sided 95% lower confidence bound of the hazard ratio of implanted 1.5 subjects to implanted secondary prevention subjects is greater than 0.70.

Analysis Methods

A Cox proportional hazard model will be used to compare the hazard rates of first appropriate VT/VF therapy between implanted subjects meeting 1.5 prevention criteria and secondary prevention subjects. Because secondary and 1.5 patients are known to be different in many potential covariates, the Cox proportional hazards model will not include any covariates. The one-sided hypothesis test will be performed by computing a 90% two-tailed confidence interval for the hazard ratio between the groups and using the lower limit of this estimated 90% CI as a rejection boundary of the null hypothesis. In particular, if the 90% CI lower limit is greater than 0.7 then the null hypothesis will be rejected.

The analysis will be performed using SAS code similar to:

```
proc phreg data = alldata;
  where group in ('A','C');
  class group (ref = 'A');
  model time2event*eventStatus(0)= group/ rl alpha = 0.1;
  run;
```

Additionally, Kaplan-Meier estimates of the survival curves will be displayed for each prevention criteria group.

Determination of Patients/Data for Analysis

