- All 1.5 prevention and secondary prevention subjects with an ICD/CRT-D implant and at least one device interrogation available in the database will be included in the primary analysis hypothesis test. This includes subjects implanted with a device after the initial enrollment period. These later implants will be included if they are secondary or 1.5 at the time of implant.
- Time 0 is the implant date and, if no events occur, subjects will be censored on the date of their latest device interrogation.
- VT/VF episodes that cannot be adjudicated (due to not saving full episode data or any other reason) will be ignored. Often, these episodes are followed by episodes that can be adjudicated, and since the endpoint is time to first episode, effects on the results from these events will be minimal. In addition, these should be balanced between the comparison groups.

Sample Size Calculation

The minimum required sample size for this study has been estimated to be 4800 subjects based on the following:

- 60% of enrollments will be secondary prevention and 40% primary prevention
- 50% of primary subjects will be in the 1.5 group
- 57% of secondary subjects will get an ICD (includes CRT-D)
- 45% of 1.5 subjects will get an ICD
- 22% of 1.0 subjects will get an ICD
- Annual attrition (includes exits and deaths) will be 10%
- The study will end two years after the last enrollment
- 4000 patients will take 2 years to enroll with enrollment beginning slowly, and then accelerating to a steady 246 per month
- Expected rates of appropriately treated VT/VF in secondary subjects follow Figure 2, with a higher rate in the first year (22.5%), then a constant rate (11.1%) thereafter
- The hazard ratio of 1.5 to secondary is 0.91

Under the above assumptions and using the hypothesis test stated above, 4800 subjects will have 80% power to reject the null hypothesis. With 4800 enrolled patients, it is expected that approximately 1650 secondary prevention subjects will be implanted, 430 1.5 prevention subjects will be implanted, and 200 1.0 subjects will be implanted.

More details, including the simulation program can be found in the Appendix.

Sample Size Re-estimation

Because most of the assumptions above are based only on investigator opinion, the sample size will be re-estimated during the study using the same simulation methods, but changing the following assumptions using the study data:

- % of enrollments will be secondary prevention

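### The power program applies 0.91 to the event probability instead of the hazard, so 4800 enrolments give about 83–84% power at HR 0.91, not 80%, and the re-estimation would carry the error forward

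*SAP*

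**What the plan says.** CIP 12.2.6 and SAP 3.2 (Sample Size Calculation) give the same planning assumption, "The hazard ratio of 1.5 to secondary is 0.91", and the same result, "4800 subjects will have 80% power to reject the null hypothesis". The decision rule in SAP 3.2 is that "if the 90% CI lower limit is greater than 0.7 then the null hypothesis will be rejected".

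SAP 5 Appendix prints the simulation program. Its header describes the parameter HRAC as a hazard ratio, and a later comment says the failure inputs were chosen to match OMNI, where the hazard ratio of C to A was 0.909. For the implanted 1.5 group the monthly event draw in year 1 is "IF D<1-(1-&FAILA12*&HRAC)(1/12) THEN FAILMONTH=MONTH", and after year 1 it is "IF D<1-(1-&FAILALONG*&HRAC)(1/12) THEN FAILMONTH=MONTH". In both lines the program raises the bracket to the power 1/12.

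The Appendix table lists power and average hazard ratio for 21 sample sizes. Every average lies between 0.902 and 0.905. The SAP comments: "HR is included because those further away from 0.91 are under-estimating power".

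On re-estimation, SAP 3.2 says that "the sample size will be re-estimated during the study using the same simulation methods". The inputs to be updated are case mix, implant rates, attrition and enrolment rate. Neither the hazard ratio nor the event rates are on the list. CIP 12.2.7 has the same list.

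**The concern.** A hazard ratio acts on the hazard, that is, on the logarithm of the event-free probability. Multiplying a cumulative probability by 0.91 gives a smaller hazard ratio, and the gap widens as the probability rises. The program therefore simulates a true effect closer to the 0.70 margin than the one the documents state, and so understates power.

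The SAP's remark on the table reads as though the shortfall were a matter of some rows lying further from 0.91 than others. It is present in all 21 rows and comes from the code.

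Two things are at stake. The claim of 80% power at 4800 under a hazard ratio of 0.91 is not what was computed. And the re-estimation would use the same method to support a decision to raise or lower N, with nothing in its list of updated inputs to remove the bias.

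**Working it through.** **Inputs** (SAP 3.2, CIP 12.2.6 and the program):
- 60% of enrolments secondary and 40% primary; half of primary subjects in the 1.5 group.
- Implant rates 57% (secondary) and 45% (1.5).
- Event probability in the secondary group 22.5% in year 1 and 11.1% per year after.
- Attrition 10% per year; two years of follow-up after last enrolment; enrolment duration as set in the program for each N (2.24 years at 4800, 2.09 at 4350).
- Success if the one-sided 95% lower bound of the C-to-A hazard ratio exceeds 0.70.

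**Hazard ratio implied by the code.** For a period with event probability p in group A, the code gives group C the probability 0.91p, so HR = ln(1 − 0.91p) / ln(1 − p).
- Year 1: 0.225 × 0.91 = 0.20475; ln(0.79525) / ln(0.775) = 0.899.
- Later years: 0.111 × 0.91 = 0.10101; ln(0.89899) / ln(0.889) = 0.905.

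**Simulation.** I rebuilt the program with the same group probabilities, monthly event and attrition draws, enrolment curve, last-visit offset and day rounding, and fitted a Cox model on group. I ran it first as printed. I then replaced `1-(1-p*0.91)**(1/12)` with `1-(1-p)**(0.91/12)`, which multiplies the hazard by 0.91. The ranges are across separate sets of runs, with Monte Carlo standard error of 0.2–0.3 points.

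| N | SAP table | Rebuilt, as coded | Hazard × 0.91 |
|---|---|---|---|
| 4000 | 73.6% | 73.8–74.1% | – |
| 4350 | 76.7% | 76.7% | 79.8–80.1% |
| 4400 | 77.7% | – | 80.3–80.5% |
| 4800 | 80.4% | 80.5–81.0% | 83.6–83.8% |
| 5000 | 82.3% | 81.6–82.3% | – |

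The rebuild reproduces the SAP's figures. As coded, the average estimated hazard ratio at 4800 is 0.904–0.905 (SAP 0.903). With the hazard scaled it is about 0.913. An average of estimated hazard ratios sits slightly above their geometric mean (0.899–0.900 as coded), so a correct program would print about 0.913. The real shortfall in the table is therefore about 0.010, not the 0.007 suggested by comparing 0.903 with 0.91.

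**Cross-check.** The Schoenfeld approximation with about 664 events and 20.8% of implanted subjects in group C gives 83.4% at HR 0.899 and 86.5% at HR 0.91. It runs high at this allocation but shows the same gap of about 3 points.

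**Effect on N.** 4350–4400 is 400–450 enrolments (8–9%) below 4800. Part of that is the SAP's own rounding up, because its table already crosses 80% between 4700 (79.9%) and 4750 (80.5%). Like for like, the code accounts for about 350 enrolments. Required events scale roughly with 1/[ln(HR/0.70)]²:
- With HR 0.900 in place of 0.91: (0.2624/0.2513)² = 1.09.
- With the simulated geometric means, 0.8992 as coded and 0.9079 corrected: (0.2601/0.2504)² = 1.08.

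**Interaction with the floor.** CIP 12.2.4 says the test is not performed with fewer than 400 implanted 1.5 subjects. The expected number is N × 0.4 × 0.5 × 0.45 = 0.09N.

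| N | Expected implanted 1.5 | Chance below 400 | Corrected power, no test counted as failure |
|---|---|---|---|
| 4350 | 391.5 | 67% | 27% |
| 4400 | 396 | 58% | 35% |
| 4800 | 432 | 5% | 80% |

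**The case against.** The strongest reply has four parts.

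First, the error is conservative and its symptom is printed. The SAP shows the average hazard ratio for every row and says that values further from 0.91 understate power, and a reader can see that all rows fall short. That stands as far as it goes. The SAP gives neither the cause nor the size, leaves the code alone, and still states 80% at 4800 under 0.91. It also chose 4800 over 4750 on differences of 0.1 to 0.6 points while a bias of about 3 points stayed in every row.

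Second, 4350 is not a usable sample size because of the floor of 400. This stands in full. The figure measures the coding error and is not a recommended target.

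Third, the effect on the re-estimation is inferred, since no re-estimation scenario was simulated, and the sponsor has discretion over N and follow-up. This is fair. The scaling argument depends little on case mix, implant rates or attrition, but the 8–9% is an approximation.

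Fourth, the gap is small beside the uncertainty in inputs that the documents say rest mostly on investigator opinion. That is true, but the re-estimation is meant to replace those opinions with data, and the coding error would remain after it had done so.

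**Conclusion.** The concern holds. On the documents' own assumptions, 4800 enrolments give about 83–84% power at a hazard ratio of 0.91. The stated 80% corresponds to a hazard ratio of about 0.90. Power of 80% at 0.91 is reached at about 4350–4400, as a power figure only.

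The trial is not under-powered by this, and the primary estimate, confidence bound, margin and alpha are untouched. The consequence lies in the re-estimation: used unchanged, the program would call for roughly 8–9% too many subjects. As an illustration, if it returned the maximum of 8000, about 590 to 660 of those enrolments would be due to the error (8000 − 8000/1.08 = 593; 8000 − 8000/1.09 = 661).

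The result rests on the printed program being the one that was run, which the match with the SAP table supports. It should be corrected before the re-estimation.

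**What to change.** In the Appendix program, apply the ratio to the hazard. For group C use `1-(1-&FAILA12)**(&HRAC/12)` in year 1 and `1-(1-&FAILALONG)**(&HRAC/12)` afterwards. For group E use the same form with `&HRAC*&HRCE` in place of `&HRAC`; those lines do not enter the A-versus-C test but carry the same fault.

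Rerun the table. Then either restate power at 4800 as about 83–84% at a hazard ratio of 0.91, or keep 80% and say that the calculation used about 0.90. Replace the remark under the table with the cause. State that the re-estimation will use the corrected program, and that any N it returns will also be checked against the floor of 400 implanted 1.5 subjects in CIP 12.2.4.

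The cost is four lines of SAS, one rerun and a restated sentence in SAP 3.2 (and in CIP 12.2.6 if it is next amended). It needs no extra patients and no change to the analysis.
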